3.2 NALBUPHINE

Nalbuphine HCl is currently available only as a generic medication in an injectable form. An injectable form of nalbuphine is a commercially available approved drug product in the United States since 1979 and originally marketed as Nubain®, on which the presently sold generic injectable formulations are based. It is currently approved for use in the United States for the relief of moderate to severe pain, a supplement to balanced anesthesia, for pre-operative and post-operative analgesia and obstetrical analgesia during labor and delivery. The European Union marketing experience with the injectable form of nalbuphine dates back to 1986 and this was recently reviewed (Nalbuphine -Medicines Evaluation Board in the Netherlands Public Assessment Report 2010).

Nalbuphine is not a controlled drug in the United States. An oral dosage form of the drug is not commercially available. Nalbuphine HCl ER is an extended release oral tablet that is currently being developed for the treatment of pruritus.

Nalbuphine is a synthetic opioid with mixed μ antagonist/ κ agonist opioid properties. Structurally, nalbuphine is a derivative of 14-hydroxymorphine and is related to the opioid μ -receptor agonist oxycodone and the opioid μ -receptor antagonist naloxone. Nalbuphine exerts its clinical pharmacologic action by competitively antagonizing the opioid μ -receptor while simultaneously acting as an agonist at the opioid κ -receptor (Gutstein 2001; Gharagozlu 2003 and 2006).

3.3 NALBUPHINE HCL ER TABLET CLINICAL DEVELOPMENT

3.3.1 Overall Summary

The safety, tolerability and pharmacokinetics of nalbuphine HCl ER tablets have been characterized following single and multiple ascending dose studies in healthy male and female human subjects, in a single dose study conducted in a dental pain patient population, a multi-dose study conducted in a patient population experiencing osteoarthritic related joint pain and in a multi-dose study conducted in both hemodialysis (HD) population experiencing uremic pruritus and healthy subjects. Studies were conducted with nalbuphine HCl ER tablets or oral solution following single dose administration from 30 mg up to 180 mg and multiple doses ranging between 30 mg BID and 180 mg BID in subjects with normal renal function (up to 3 weeks) and in the hemodialysis population in multiple doses ranging from 30 mg BID to 240 mg BID (up to 15 days).

In subchronic and chronic dose toxicology studies, the CNS was identified as the only target organ when unformulated (neat) nalbuphine was given to dogs at high doses. High systemic drug exposures in dogs caused CNS toxicity (tremors and convulsions) leading to deaths in some cases. It should be noted that the convulsions at high doses of nalbuphine in dogs were most likely C_{max} -related. In toxicology studies in which dogs were given high doses of nalbuphine formulated with release-rate controlling excipients that blunt the C_{max} , no CNS signs of toxicity were observed. Using the most conservative (lowest) margin of safety determined in all toxicity studies, a minimum 12.4-fold safety margin was calculated respectively for the mean plasma C_{max} in subjects with normal renal function at the highest projected clinical dose of nalbuphine (180 mg BID) relative to the plasma C_{max} at the lowest NOAEL in dogs given unformulated nalbuphine. Convulsions were not observed in any of the clinical trials conducted with nalbuphine HCl ER oral tablets in subjects with normal renal function at doses up to 180 mg BID (360 mg daily dose) or in HD patients at doses up to 240 mg BID (480 mg daily dose).

In the course of development, 355 subjects received at least one dose of oral nalbuphine HCl. The most frequently reported adverse events were primarily in the Central Nervous System (CNS) and Gastrointestinal (GI) organ system categories. All these side effects are known to occur with drugs with opioid pharmacologic properties. Most of the side effects noted in the study program were mild to moderate in severity. Initiating drug dosing in both HD patients and healthy subjects at the 30 mg BID dose resulted in good tolerability for subsequent titration related dose escalation.

No drug abuse issues were reported during any of the investigations. The incidence of opiate withdrawal effects noted at drug discontinuation in the patients was investigated in

the osteoarthritis pain treatment study when nalbuphine dosing was abruptly stopped following the end-of-study participation. There was an absence of any objective evidence of physical withdrawal symptoms in 85% of the patients and only mild evidence of physical withdrawal symptoms in the remainder of the patients.

3.3.2 Clinical Study TR01 in Hemodialysis Patients and Healthy Volunteers

Pruritus is a frequently identified sign and symptoms of uremia (“uremic pruritus”) and is thus a common symptom in patients receiving hemodialysis (Pisoni et al 2006 and Narita et al 2006). Study TR01 was undertaken to assess the safety, PK, and the open label effects on pruritus intensity in hemodialysis subjects. PK and safety was compared to matched healthy control subjects.

Study TR01 was a single site, open label, non-randomized, parallel group, escalating dose study in hemodialysis patients with pruritus of at least mild intermittent intensity receiving intermittent hemodialysis three times a week compared to matched healthy control patients. All subjects were in house during the entire dosing period. Nalbuphine HCl ER tablets were administered orally for up to a 15 day period in HD subjects and 13 days in healthy subjects. Doses were sequentially escalated from 30 mg QD on Day 1 to 30mg BID then to 60 mg BID, 120 mg BID, 180 mg BID and 240 mg BID with dose escalation predicated on PK, safety, and tolerability of the preceding dose. HD subjects remained at each dose level for 2-3 days for a minimum of 4-5 consecutive doses. Healthy subjects remained at each dose level for 3-4 days for a minimum of 5 consecutive doses.

Study subjects were separated into 2 cohorts: Of the 15 HD subjects in enrolled into Cohort 1, 11 were assigned to dose escalate up to 180 mg BID and 4 were assigned to dose escalate up to 240 mg BID. 13 subjects (11 males and 2 females) completed the study. One male subject discontinued secondary to non-drug related disease progression diagnosis of pleural effusion at the 30 mg BID dose level and a female subject discontinued following a Grade 3 AE of vertigo at the 240 mg BID dose level. Cohort 2 were healthy subjects who were assigned to dose escalate up to 180 mg BID. Cohort 2 consisted of 8 healthy subjects (6 males and 2 female) who completed the study and one male subject who discontinued at the 120 mg BID dosing level with only Grade 1 intensity AEs. All study subjects were closely monitored for AEs throughout the study.

In healthy subjects, the dosing regimen resulted in mainly Grade 1 AEs and the dose escalation was tolerable in 8/9 subjects dosed. Of the nine healthy subjects enrolled, one subject withdrew from the study secondary to AE Grade 1 level gastrointestinal reflux, nausea/vomiting and vertigo symptoms at the 120 mg BD dosing level. The subject recovered from the AE following drug discontinuation. AEs that occurred in greater than two subjects were somnolence (N=2), headaches (N=2), flatulence (N=2) and constipation (N=3).

In the HD subjects, there were no deaths or drug-related serious AEs. There were no dose-limiting AEs reported as defined as two HD subjects experiencing a drug-related AE of Grade 3. A total of 72 AEs were reported in the 15 HD subjects of Cohort 1. The nervous and gastrointestinal organ systems had the highest incidence of AEs. The most frequently occurring AEs were nausea and somnolence. Of the 13 HD subjects who completed the study (10 HD patients assigned to dose up to 180 mg BID and 3 HD subjects assigned to

dose up to 240 mg BID), 12 subjects completed the trial per protocol and 1 subject completed the study but did not dose titrate beyond 120 mg BID.

With regard to the gastrointestinal organ system, of the 14 HD subjects who completed 13 days of dosing (1 subject at 120 mg BID and 13 subjects at 180 mg BID), 4/14 (29%) experienced no nausea during the study and 7/14 (50%) experienced Grade 1 intensity nausea that was self-limited and only occurred at the initiation dose of 30 mg. One subject (1/14, 7%) experienced Grade 2 nausea starting from the 60 mg BID through the 180 mg BID dose. Three subjects (3/14, 21%) only developed nausea at the 180 mg dose level.

With regard to the nervous system AEs, of the 14 HD subjects who completed the 13 days of dosing, 5/14 (36%) did not experience somnolence, 4/14 (29%) experienced somnolence that was self-limited and only occurred at the initiation dose of 30 mg. With regards to AE intensity, two subjects (2/14, 14%) experienced somnolence of Grade 2 intensity at dosing levels above 30 mg BID. Only one drug-related Grade 3 AE (vertigo) was reported in one subject at the 240 mg dose which resolved completely following drug termination. No clinically relevant findings in vital signs, blood pressure (BP), ECGs or physical examinations were noted during the study. Oxygen saturation was also monitored via pulse oximetry as a safety precaution. The oximetry readings were taken at regular intervals during the daytime and continuously monitored during the nighttime hours over the 15 days of drug dosing and up to a maximal dose of 240 mg BID.

In both the HD and healthy subjects, no clinically significant decrease in daytime readings were recorded in the oximetry readings except in the one male HD subject previously mentioned who discontinued from the study at the time of the development of a pleural effusion. There was no clinically significant decrease in the nocturnal oxygen saturation level below the pre-dosing baseline nocturnal oxygen saturation level in any HD subject.

The Investigator's Brochure and Section 5.4.4.4; Table 21 and Section 5.4.4.2.2; Table 17 summarizes the AE profile of the TR01 HD subjects and healthy subjects respectively.

During the course of TR01, the 15 HD subjects that were enrolled were on multiple concomitant medications. Common concomitant medications included heparin, vitamin D, aspirin, iron, hyperphosphatemia management with sevelamer, erythropoiesis-stimulating agent, secondary hyperparathyroidism management with cinacalcet, neuropathic pain management with gabapentin; antihypertensive medications such as amlodipine (calcium channel blocker), carvedilol (beta and alpha-1 blocker), metoprolol (beta blocker), lisinopril (ACE inhibitor); gastrointestinal medications: omeprazole, pantoprazole, ranitidine and renal vitamins and supplements. These medications seem to be commonly used by HD patients both in the US and the EU (Schmid et al 2010). There was no clinically significant difference in the adverse event profile observed based on concomitant medication use or obvious pharmacodynamic interaction over the course of the study.

Data on Itch Intensity was obtained in an unblinded fashion from the HD subjects enrolled in the open-label single arm Study TR01 using a 0 (none) to 10 cm (maximal possible intensity) itch Visual Analogue Scale (VAS) recording "worst itch" intensity. From a baseline mean daytime VAS of 4.4 ± 2.3 cm and nighttime of 2.8 ± 2.1 cm, the mean VAS decreased over a 13-day dosing period by -3.6 ± 2.5 cm and by -1.8 ± 2.1 cm, respectively.

Please see the Investigator's Brochure for more details on the TR01 study.

3.3.3 Additional Nalbuphine HCl ER Tablet Clinical Data

In addition to the subjects in the TR01 study, a total of 331 subjects have been exposed to nalbuphine HCl during the course of 8 previous clinical studies.

Four Phase 1 studies were early biopharmaceuticals studies conducted in healthy subjects mainly for formulation selection and as such they support the safety of the drug product. In addition, two Phase 1 studies were conducted with the current clinical formulations and each consisted of a single dose study assessing the safety, tolerability, and PK of the current tablet formulations in the 30 mg -180 mg range.

A safety and efficacy analgesic study was conducted in subjects with dental-pain following third molar extractions following a single dose (placebo or 60 mg or 120 mg). The subjects were otherwise healthy male and female subjects. The study also contained PK-PD analysis demonstrating an analgesic dose-response relationship, with clear differentiation between the nalbuphine dose groups and placebo group.

Oxygen saturation was monitored via pulse oximetry as a safety precaution during Phase 1 studies and in the single dose third molar extraction dental pain treatment study. All subjects who received the drug had oxygen saturation levels within the 90%-100% range during the studies.

A safety and efficacy analgesic study was conducted in a patient population experiencing osteoarthritic related joint pain using the current nalbuphine HCl ER 60 mg tablet. The population was demographically older with the mean age of 57 years and a range extending from age 40-70 years. Subjects were dosed continuously for up to 3 weeks starting at 60 mg BID up to a dose of 180 mg BID. Subjects who tolerated the initial dosing were titrated up in weekly increments of 60 mg BID to the maximal dose of 180 mg BID. The AEs that developed mainly had their onset at the initiation of dosing with no new type of AE developing in any statistically significant incidence during the course of dose escalation.

In both genders, the most frequently reported adverse events were primarily in the Central Nervous System and Gastrointestinal organ system categories. A higher incidence of AEs was noted in females during week one of dosing with the gender asymmetry in AE generation lessening as a function of time. This difference in AE incidence may be related to the tendency of females to have higher plasma levels than males (about 1.7 and 1.3 fold higher for C_{max} and AUC, respectively). Nalbuphine total systemic clearance is reported to decrease with age leading to a higher absolute bioavailability (~ 44%) in elderly subjects (older than 65 years) relative to younger adults (11%) following oral administration (Jaillon, 1989).

In these eight clinical studies overall, the most frequently reported AEs in the single dose and multi-dose studies were CNS events, namely dizziness, headache, and somnolence. Gastrointestinal system AEs were mainly nausea and vomiting. Most of the AEs noted in the clinical study program were mild to moderate in severity.

In the case of single dose Phase 1 nalbuphine HCl ER tablet administration, there was a dose relationship to the incidence of AEs and there was minimal AEs observed at the 30 mg dose compared to initiating dosing at the higher doses. As a result, a titration to higher doses from a starting dose of 30 mg was selected for subsequent studies that also included TR01 in order to improve the tolerability of the drug.

Section 5 of the Investigator's Brochure summarizes the results of the clinical development program in detail.

4 STUDY OBJECTIVES

4.1 PRIMARY OBJECTIVE

The primary objective of the study is:

- To evaluate the safety and tolerability of nalbuphine HCl ER tablets during a drug treatment period of up to 50 weeks.

4.2 SECONDARY OBJECTIVES

The secondary objectives of the study are to evaluate the effect of nalbuphine HCl ER tablets on:

- To evaluate the safety of nalbuphine HCl ER by achieved maintenance dose at the end of Treatment Week 4
- Assess skin lesion improvement using the metrics of the PAS
- Change from Baseline in Patient-Reported Outcome measures Worst (i.e., most severe itching over the past 24 hours) itch NRS, average itch intensity NRS, VRS (itchy, burning and stinging), MOS Sleep-R, ItchyQoL, HADS by the final Treatment Period Visit
- Change between Baseline and the final Treatment Period Visit in PBI-P
- A description of the percentage of patients utilizing various doses of nalbuphine HCl ER tablets by Study Week
- A description of the frequency and reasons for dose up and down-titration and treatment discontinuation during the study
- Frequency and distribution by time on study of patients determined to meet failure-to-improve criteria
- Changes in the PRO measurements during the Washout Period after cessation of treatment of nalbuphine HCl ER tablets
- Time to first use of rescue medications and the number of days of use of rescue medications for itching
- To evaluate the daily changes in the Subjective Opiate Withdrawal Scale (SOWS) during the Washout Period after cessation of treatment of nalbuphine HCl ER tablets

4.3 EXPLORATORY OBJECTIVES

- The potential of nalbuphine HCl ER tablets to impact on the measurement of nerve fiber density (histology) and MOR/KOR density (histology, Western Blot) and Histological (H&E) changes in skin biopsies taken Baseline and the final Treatment Period Visit to investigate possible correlation with any clinical response and also

compared to biopsy material assessed during study TR03 (optional procedure at select sites only).

5 STUDY ENDPOINTS

5.1 PRIMARY ENDPOINT

- A description of the incidence and nature of TEAEs during Treatment Weeks 5-50

5.2 SECONDARY ENDPOINTS

Visit 1a or 1b will serve as the baseline visit for efficacy endpoints. Visit 1a will be the baseline for patients directly entering the Treatment Period as of Visit 1a. Visit 1b will be the baseline for patients entering the Treatment Period after participating in the Observation Period for any length of time.

- Assess skin lesion improvement using the metrics of the PAS
- Change from Baseline in Patient-Reported Outcome measures Worst itch NRS, average itch intensity NRS, VRS (itchy, burning and stinging), MOS Sleep-R, ItchyQoL, HADS) by Treatment Period study visit and Baseline NRS score
- Change between Baseline and the final Treatment Period visit in PBI-P
- A description of the percentage of patients utilizing various doses of nalbuphine HCl ER tablets by Study Week
- A description of the frequency and reasons for dose up- and down-titration and treatment discontinuation during the study
- Frequency and distribution by time on study of patients determined to meet failure-to-improve criteria
- Changes in the PRO measurements during the Washout Period after cessation of treatment of nalbuphine HCl ER tablets
- Time to first use of rescue medications and the number of days of use of rescue medications for itching
- To evaluate the daily changes in the Subjective Opiate Withdrawal Scale (SOWS) during the Washout Period after cessation of treatment of nalbuphine HCl ER tablets.

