9.6.2.2.12 TV 14 (End of Treatment Visit)

This visit applies to all patients who completed TV13; including patients who met Failure-to-Improve criteria at any Treatment Visit during the study (unless consent is withdrawn).

For patients who DID NOT meet Failure-to-Improve criteria during the conduct of the study, this visit (TV14) takes place after the patient has completed dosing with study medication.

- For patients who entered the Treatment Period at Visit 1a, TV14 will take place during week 51; four (4) weeks after TV13, as these patients should complete 50 weeks of treatment prior to TV14
- For patients who entered the Treatment Period at Visit 1b see [Table 8](#) for information on when TV14 is to take place

The following procedures are to take place at this visit:

- complete PAS
- obtain vital signs
- perform physical examination
- perform brief neurological assessment
- complete the PAS

- perform 12-lead ECG after at least 5 minutes in a supine position (See the Study Reference Manual for ECG procedures, [Section 17.4](#) Electrocardiograms for the handling of Cardiovascular adverse events)
- collect blood for central laboratory (hematology and chemistry) and serum pregnancy test (regardless of sexual activity) for central laboratory
- collect urine for urinalysis at the central laboratory
- collect blood for PK
- perform skin biopsy (optional procedure at select sites only). Obtain 3 samples (i.e., H&E, nerve fiber density (histology) and MOR/KOR density (histology, Western Blot)); see the Lab and Study Reference Manuals for details
- administer PRO measurements (paper versions):
 - Worst itch NRS
 - Average itch intensity NRS
 - VRS
 - ItchyQoL
 - MOS Sleep-R
 - HADS
 - SOWS

The PRO questionnaires must be administered at the study site under the supervision of and by trained study staff, strictly adhering to PRO Administration Instructions (see Study Reference Manual).

- record AEs
- review of concomitant medications, including over-the-counter medications, nutritional supplements, and vitamins
- perform study drug accountability, final retrieval of any previously dispensed study drug
- retrieve the Dosing Diary
- Dispense the 14 Day SOWS packet, instruct the patient on how to complete the scales and to complete the scales daily for 14 days
- Schedule the patient for the Washout and Safety Follow-up Period Visit

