9.7.7.6 Patient Benefit Index (PBI-P)

The PBI-P questionnaire assesses the importance of treatment objectives to the individual. Before, and at the end of drug treatment in this study, the patient completes the same questionnaire and rates the extent to which the treatment objectives have been achieved. The instrument consists of 27 multiple choice questions that can be answered “not at all”, “somewhat”, “moderately”, “quite” and “very”. The instrument can be found in [Appendix 4](#).

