19.8 EFFICACY ANALYSES

19.8.1 Efficacy Population

The Safety population, consisting of all enrolled patients who have received a single dose of study medication, will be used to evaluate the efficacy endpoints defined for this study. Eligibility for analysis of a particular endpoint will require only that the patient have a baseline value and at least one post-baseline value for the endpoint of interest, so that a change from baseline calculation can be obtained. All efficacy endpoints will be evaluated through the generation of descriptive summary statistics. For continuous variables, the mean, standard deviation, median, minimum, and maximum will be presented for a particular visit and for the change from baseline (Visit 1a or 1b). For categorical variables, the number and percentage of patients within each category of classification will be summarized by study visit. No formal statistical testing will be conducted.

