
7. Activity. Please mark the stage.
 
  
 	stage 0	stage 1	stage 2	stage 3	stage 4	
   
 Prurigo lesions with excoriations/crusts compared to all prurigo lesions	0 %	1- 25 %	26 - 50 %	51 - 75 %	76 - 100 %	
 
 Healed prurigo lesions compared to all prurigo lesions	100 %	75-99 %	50 - 74 %	25 - 49 %	0 - 24 %	
  
			stage 0	stage 1	stage 2	stage 3	stage 4	Prurigo lesions with excoriations/crusts compared to all prurigo lesions	0 %	1- 25 %	26 - 50 %	51 - 75 %	76 - 100 %	Healed prurigo lesions compared to all prurigo lesions	100 %	75-99 %	50 - 74 %	25 - 49 %	0 - 24 %
	stage 0	stage 1	stage 2	stage 3	stage 4														
Prurigo lesions with excoriations/crusts compared to all prurigo lesions	0 %	1- 25 %	26 - 50 %	51 - 75 %	76 - 100 %														
Healed prurigo lesions compared to all prurigo lesions	100 %	75-99 %	50 - 74 %	25 - 49 %	0 - 24 %														

8. Take photos of the patient: Overview front and back, area(s) of marked monitor lesions to recognize on next visit
																			

Patient Benefit Index, Pruritus Version (PBI-P)

Sample – actual assessment scale will be provided to the patient at appropriate visits

Importance of Treatment Goals

With the help of the following questions, we'd like to know how important the goals mentioned below are to you personally in the **current treatment** of your skin disease.

For each of the following statements, please mark **how important** this treatment goal is to you.

If a statement does not apply to you, for example because you are not experiencing pain, please mark "does not apply to me".

As a result of therapy, how important is it for you to...		not at all	somewhat	moderately	quite	very	does not apply to me
1	...be free of pain						
2	...be free of itching						

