17	...be able to lead a normal working life						
18	...be able to have more contact with other people						
19	...be more comfortable showing yourself in public						
20	...be less burdened in your partnership						
21	...be able to have a normal sex life						
22	...be less dependent on doctor and clinic visits						
23	...need less time for daily treatment						
24	...have fewer out-of-pocket treatment expenses						
25	...have fewer side effects						
26	...find a clear diagnosis and therapy						
27	...have confidence in the therapy						

Please recheck your answers to make sure you have clearly marked each statement with an "x".

Thank you very much for your cooperation!

PBI-P (Cont'd)

Sample – actual assessment scale will be provided to the patient at appropriate visits

Treatment Benefits

When the treatment began, you indicated in a questionnaire how important various goals were in the treatment of your skin disease.

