Please mark each of the following statements according to the extent to which those treatment goals **were achieved**, indicating if the treatment has benefited you. If a statement did not apply to you, for example because you did not experience any pain, please mark "did not apply to me".

The current treatment has helped me to ...		not at all	somewhat	moderately	quite	very	did not apply to me
1	...be free of pain						
2	...be free of itching						
3	...no longer have burning sensations on my skin						
4	...be healed of all skin defects						
5	...concentrate better						
6	...be less nervous						
7	...be able to wear all types of clothing						
8	...be able to bathe and shower normally						
9	...sleep better						
10	...feel less depressed						
11	...experience greater enjoyment of life						
12	...have no fear that the disease will get worse						

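### The PBI-P endpoint is worded as a change from Baseline although its two forms rate different things, and the TV14 procedure list omits the PBI-P

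*Protocol*

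**What the plan says.** **The endpoint.** Section 5.2 lists "Change between Baseline and the final Treatment Period visit in PBI-P". The synopsis (secondary objectives and study endpoints) and Section 4.2 word it in nearly the same way. Section 19.8.1 asks for a baseline and a post-baseline value of each efficacy endpoint "so that a change from baseline calculation can be obtained".

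**The instrument in the body text.** Section 9.7.7.6 first says that the PBI-P concerns the importance of treatment objectives. It then says that before and at the end of drug treatment "the patient completes the same questionnaire and rates the extent to which the treatment objectives have been achieved".

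**The instrument in Appendix 4.** There are two forms with 27 matching goals.
- Importance of Treatment Goals explains that the study team would "like to know how important the goals mentioned below are to you personally in the" current treatment. Its stem is "As a result of therapy, how important is it for you to" followed by each goal.
- Treatment Benefits opens with "When the treatment began, you indicated in a questionnaire how important various goals were in the treatment of your skin disease". It then instructs: "Please mark each of the following statements according to the extent to which those treatment goals" were achieved.

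**The timing.** Table 4 and Sections 9.6.1 and 9.6.4 place the PBI-P at Visit 1a/1b. Table 6 places it at TV14 and at the Early Termination visit, and Section 9.6.7 lists it for the latter. The TV14 procedure list in Section 9.6.2.2.12 names seven patient-reported instruments (two itch NRS scales, VRS, ItchyQoL, MOS Sleep-R, HADS and SOWS). The PBI-P is not among them.

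**The concern.** A change score needs the same quantity measured on two occasions. Here the first form measures what the patient wants from treatment and the second measures what the patient got. If the endpoint is programmed as written, the result mixes the two. Patients who began with high expectations would tend to show negative values even when treatment helped them, and a reader of the study report would naturally take a negative mean as deterioration.

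The collection gap is a separate matter. TV14 is the only scheduled post-baseline PBI-P for a patient who does not withdraw consent. That includes patients stopped for failure to improve, who are sent to the TV14 procedures. Section 19.3 rules out imputation, so a form not handed out at TV14 is lost to the analysis.

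**Working it through.** The protocol states no figure for this endpoint, so there is nothing to reproduce. The check has three steps.

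**Step 1: what could be subtracted.** Three readings are possible.
- *Importance form first, Benefits form last.* This is what the Benefits form's own opening implies. The difference is benefit minus importance, which is not a change in either.
- *Importance form both times.* The difference is a change in how much the goals matter. It says nothing about benefit.
- *Benefits form both times.* At Visit 1a/1b the patient would rate what a treatment not yet started in this study has achieved, on a form that refers back to an importance questionnaire.

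Only the first reading fits Appendix 4. None gives an interpretable change in benefit.

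**Step 2: how benefit minus importance behaves.** Assumption: both forms use the same codes, 0 (not at all) to 4 (very). The protocol gives only the verbal answers. For one goal, difference = benefit − importance.

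| Importance | Lowest difference (benefit 0) | Highest difference (benefit 4) |
|---|---|---|
| 0 | 0 | 4 |
| 1 | -1 | 3 |
| 2 | -2 | 2 |
| 3 | -3 | 1 |
| 4 | -4 | 0 |

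- Of the 5 × 5 = 25 answer pairs, five give 0: (0,0), (1,1), (2,2), (3,3) and (4,4), written as importance then benefit. An unimportant goal with no benefit and a vital goal fully achieved are indistinguishable.
- The order can reverse. Importance 4 with benefit 3 gives 3 − 4 = -1. Importance 0 with benefit 1 gives 1 − 0 = +1. The first patient reports more benefit on a goal that matters and gets the lower score.
- The zero does not depend on the 0 to 4 codes. With any common ordered coding, equal answers cancel, and a goal given the top importance rating cannot exceed 0.
- Both forms also offer a not-applicable answer, which Section 9.7.7.6 does not mention. A difference is undefined there.

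**Step 3: the same patients on a level score.** Take importance 4 on all 27 goals and benefit b on all 27, with weighted benefit = Σ(importance × benefit) / Σ(importance) = (27 × 4 × b) / (27 × 4) = b.

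| Benefit b | Mean difference (b − 4) | Weighted benefit |
|---|---|---|
| 0 | -4 | 0 |
| 2 | -2 | 2 |
| 4 | 0 | 4 |

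The weighted score reads directly as benefit. The difference presents complete success as no change. This formula is an illustration and does not come from the protocol.

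**The case against.** **Scoring belongs in the SAP.** The protocol nowhere prescribes item-level subtraction, and Section 19.1 defers detailed methods to a SAP. It stands that the absence of a scoring rule is no fault. But the protocol itself fixes the endpoint as a change, in four places. A SAP can define a sound PBI-P score only by departing from that wording.

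**Section 9.7.7.6 is merely loose.** It names importance as well as achievement, and the 27 goals match across the forms. That is fair as to intent. The statement that one questionnaire serves at both times is still wrong against Appendix 4, and it is the sentence that a reader would use to justify a change score.

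**Sites will follow the schedule.** A reader might infer from the TV14 list that the second form would never be collected. The documents do not support that: Section 9.7.7 has the instruments given according to the Schedule of Events, Table 6 includes the PBI-P at TV14, and Section 9.7.7.6 mentions the end of treatment. What remains is a conflict between one visit list and the schedule, with partial and site-dependent loss.

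**The PBI-P is worthless here.** This too might be inferred, and it goes too far. The difference lacks meaning; the two forms, used together, do not.

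**Conclusion.** The point holds. As worded, the PBI-P endpoint is a difference between importance and benefit, and that difference cannot be interpreted. The conclusion rests on the two forms in Appendix 4 and on their being coded alike; the specific values above rest on the assumed 0 to 4 coding. Section 9.7.7.6 contradicts Appendix 4, and Section 9.6.2.2.12 contradicts Table 6, which puts end-of-treatment forms at risk at sites that work from the visit text.

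Severity is moderate. A reader might take this as a defect that threatens the study's conclusions, but the documents do not support that. The primary endpoint is treatment-emergent adverse events, the PBI-P is one of nine secondary endpoint bullets, about 60 patients at most are expected, and no formal testing is planned.

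**What to change.** 1. In the synopsis (secondary objectives and study endpoints) and in Sections 4.2 and 5.2, replace the change with a PBI-P benefit score at the end of treatment that uses the baseline importance ratings, summarised as a level. An importance-weighted mean benefit over applicable goals is one example. Confirm the formula, and the handling of not-applicable answers, against the instrument's scoring instructions. Section 19.8.1 already provides summaries at a particular visit, so a level fits there.
2. In Section 9.7.7.6, state that the Importance of Treatment Goals form is given at Visit 1a/1b and the Treatment Benefits form at TV14 or Early Termination, and delete the statement that the questionnaire is the same.
3. Add the Treatment Benefits form to the TV14 list in Section 9.6.2.2.12.

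The cost is wording in six places (4 + 1 + 1). No instrument, visit or patient is added, since both forms are already in Appendix 4. The third item is the urgent one, because a form missed at TV14 is not replaced by imputation.
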